## Document History

Document	Version Date
Amendment 1	19 April 2023
Original protocol	17 March 2023

This amendment incorporates all revisions to date, including amendments made at the request of country health authorities and IRBs/ECs and any global protocol administrative change letter(s).

## Protocol Amendment Summary of Changes Table

### Amendment 1 (19 April 2023)

#### Overall Rationale for the Amendment:

To include drug-product acceptability assessment following the dose of PF-07817883

Description of Change	Brief Rationale	Section # and Name
Substantial Modification(s)		
Added the activity of “drug-product acceptability”.	Updated to reflect the change in schedule of activities	Section 1.3 Schedule of Activities and Section 10.9 Appendix 9 Drug Product Acceptability Questionnaire.
Added 1 exploratory endpoint for the evaluation of acceptability of PF-07817883 in healthy participants.	Updated to reflect the addition of an exploratory endpoint	Section 3 Objectives and Endpoints
Added the drug-product acceptability questionnaire to the study design of Period 1.	To assess acceptability of the formulation	Section 4.1 Overall Design
Non-substantial Modification(s)		
Corrected the visit identifier in the SoA Table 1	Corrected errors	Section 1.3 Table 1
Added “at the site” in “administration of study intervention(s) at the site”	Updated per changes in protocol template for clarification	Section 6.1.1 Administration
Updated the potential cases of acute kidney injury, and	Updated per changes in protocol template	Section 7.1.1 Potential Cases of Acute Kidney

Description of Change	Brief Rationale	Section # and Name
the assessment of kidney function		Injury, Section 10.7.1 Laboratory Assessment of Change in Kidney Function and Detection of Kidney Injury, and Section 10.7.3 Adverse Event Grading for Kidney Safety Laboratory Abnormalities
Updated the time period for SAE collection	Updated per changes in protocol template	Section 8.4.1 Time Period and Frequency for Collecting AE and SAE Information
Removed “DP-005806 or DP-005808” from the current name of the study intervention	PACL dated 07 Apr 2023	Section 6.1 Study Intervention(s) Administered
Removed “Only if urine dipstick is positive for blood, protein, nitrites, or leukocyte esterase and culture only if bacteriuria” from footnote b in Table 7	PACL dated 07 Apr 2023	Section 10.2 Appendix 2: Clinical Laboratory Tests

## 1. PROTOCOL SUMMARY

### 1.1. Synopsis

**Protocol Title:** A Phase 1, Open-Label, 2-Period, Fixed Sequence Study to Estimate the Effect of Itraconazole on the Pharmacokinetics of PF-07817883 in Healthy Adults

**Brief Title:** A Study to Learn About How Itraconazole Affects the Blood Level of Study Intervention PF-07817883 in Healthy Adults

### Regulatory Agency Identification Number(s):

US IND Number:	162644
EudraCT Number:	NA
ClinicalTrials.gov ID:	NA
Pediatric Investigational Plan Number:	NA
Protocol Number:	C5091008
Phase:	1

### Rationale:

PF-07817883 is a potent and selective inhibitor of the SARS-CoV-2 Mpro that is currently being developed as an oral treatment of COVID-19.

In vitro and in vivo (in rats) metabolite profiling suggests that the primary metabolic route for PF-07817883 is CYP-mediated oxidation. In vitro studies using human liver microsomes indicated metabolism of PF-07817883 was predominantly mediated by CYP3A4 CCI [REDACTED].

The purpose of this study is to estimate the effect of a strong inhibitor of CYP3A4 on the PK of PF-07817883 in healthy adult participants. Results of this study will provide guidance for dosing recommendations with concomitant medications that have CYP3A inhibitory potential.

## Objectives and Endpoints:

Objectives	Endpoints
Primary: 

To estimate the effect of multiple doses of itraconazole 200 mg QD on the PK of PF-07817883 following a single oral dose of PF-07817883 300 mg

	Primary: 

PF-07817883 plasma PK parameters: <math>C_{max}</math> and <math>AUC_{inf}</math> (if data permits, otherwise <math>AUC_{last}</math>) with itraconazole (test) versus without itraconazole (reference)

Secondary: 

To evaluate the safety and tolerability of PF-07817883 in healthy participants in the absence and presence of multiple doses of itraconazole

To characterize additional PK parameters of PF-07817883 when administered alone or with itraconazole in healthy participants

	Secondary: 

Assessment of TEAEs, clinical laboratory abnormalities, vital signs, physical exams, and 12-lead ECGs

PF-07817883 plasma PK parameters: <math>T_{max}</math>, and if data permits, <math>t_{1/2}</math>, <math>CL/F</math>, <math>V_{d}/F</math>, with and without coadministration of itraconazole

## Overall Design:

This is a Phase 1, open-label, 2-period, fixed sequence study to estimate the effect of itraconazole, a strong CYP3A4 inhibitor, on the plasma PK of PF-07817883 in healthy adults. The study will consist of 2 treatments: a single oral dose of PF-07817883 300 mg alone and a single oral dose of PF-07817883 300 mg in combination with multiple oral doses of itraconazole 200 mg QD. A total of approximately 12 healthy adults will be enrolled to ensure at least 10 participants complete the study. Participants who discontinue from the study for non-safety reasons may be replaced at the sponsor's discretion in collaboration with the investigator.

Healthy participants will be screened to determine eligibility within 28 days prior to study treatment. Medical history and results of physical examination, physical measurements, vital signs, 12-lead ECGs, and clinical laboratory evaluations will determine eligibility. Participants will report to the PCRU on Period 1 Day -1 (Study Day -1) and will be required to stay in the PCRU for 13 days and 12 nights.

In Period 1, each enrolled participant will receive a single oral dose of PF-07817883 300 mg in the morning of Day 1. Serial plasma PK samples will be collected up to 96 hours and urine will be collected up to 24 hours after PF-07817883 dose on Day 1.

Participants will receive itraconazole 200 mg administered orally QD on Period 2 Days 1-7 (Study Days 5-11), inclusive. Participants will receive a single oral dose of PF-07817883 300 mg in the morning of Period 2 Day 4 (Study Day 8). Following the administration of PF-07817883 on Period 2 Day 4, participants will undergo serial PK sampling up to 96 hours and urine collection up to 24 hours. As a result, the washout interval between dosing of PF-07817883 in Period 1 and Period 2 is 7 days. Participants may be confined at the PCRU

during the entire duration of the study, and they will be discharged from the PCRU on Period 2 Day 8 (Study Day 12) following completion of all assessments.

A follow-up (which may be a phone call) will be made to participants approximately 28 to 35 days from administration of the final dose of study intervention.

**Number of Participants:**

Approximately 12 participants will be enrolled in the study.

Note: "Enrolled" means a participant's, or their legally authorized representative's, agreement to participate in a clinical study following completion of the informed consent process and assignment to study intervention. A participant will be considered enrolled if the informed consent is not withdrawn prior to participating in any study activity. Potential participants who are screened for the purpose of determining eligibility for the study, but do not participate in the study, are not considered enrolled, unless otherwise specified by the protocol.

**Study Population:**

Key inclusion and exclusion criteria are listed below:

**Inclusion Criteria**

Participants must meet the following key inclusion criteria to be eligible for enrollment into the study:

**Age and Sex:**

1. Male and female participants aged 18 to 65 years of age, inclusive, at screening who are overtly healthy as determined by medical evaluation including medical history, physical examination, laboratory tests, and standard 12-lead ECG.

**Other Inclusion Criteria:**

2. BMI of 17.5 to 32 kg/m^2; and a total body weight >50 kg (110 lb).
3. Capable of giving signed informed consent.
4. Willing and able to comply with all scheduled visits, treatment plan, laboratory tests, lifestyle considerations, and other study procedures.

## **Exclusion Criteria**

Participants with any of the following characteristics/conditions will be excluded:

### **Medical Conditions:**

1. Any medical or psychiatric condition including recent (within the past year) or active suicidal ideation/behavior or laboratory abnormality or other conditions that may increase the risk of study participation or, in the investigator's judgment, make the participant inappropriate for the study.
2. Evidence or history of clinically significant hematological, renal, endocrine, pulmonary, gastrointestinal, CV, hepatic, psychiatric, neurological, or allergic disease (including drug allergies, but excluding untreated, asymptomatic, seasonal allergies at the time of dosing) and, in the judgment of the investigator, would make the participant inappropriate for entry into this study.
3. Any condition possibly affecting drug absorption (eg, gastrectomy, cholecystectomy).
4. Positive test result for SARS-CoV-2 infection at admission.

### **Prior/Concomitant Therapy:**

5. Use of prescription or nonprescription drugs and dietary and herbal supplements within 28 days or 5 half-lives (whichever is longer) prior to the first dose of study intervention (refer to Section 6.9 for additional details).
6. Participants who have received a COVID-19/flu vaccine(s) within 7 days before screening or admission, or who are to be vaccinated with a COVID-19/flu vaccine(s) at any time during the study confinement period.

### **Prior/Concurrent Clinical Study Experience:**

7. Participation in other studies involving study intervention within 30 days or 5 half-lives (whichever is longer) prior to study entry. A participant may be eligible even if they are in the follow-up phase of an investigational study as long as they have not received treatment in that study for at least 1 month.

### **Diagnostic Assessments:**

8. A positive urine drug test. A single repeat for positive drug screen may be allowed.
9. Pregnant or breastfeeding women or evidence of positive pregnancy test at screening or Study Day -1.
10. History of HIV infection, hepatitis B, or hepatitis C; positive testing for HIV, HBsAg, or HCVAb. Hepatitis B vaccination is allowed.

11. Participants with ANY of the following abnormalities in clinical laboratory tests at screening, as assessed by the study-specific laboratory and confirmed by a single repeat test, if deemed necessary:
  - AST or ALT level  $\geq 1.5 \times$  ULN;
  - T bili level  $\geq 1.5 \times$  ULN; participants with a history of Gilbert's syndrome may have direct bilirubin measured and would be eligible for this study provided the direct bilirubin level is  $\leq$ ULN.
12. Renal impairment as defined by an eGFR in adults of  $<75$  mL/min. Based upon participant age at screening, eGFR or eCrCl is calculated using the recommended formulas in Section 10.7.2 to determine eligibility and to provide a baseline to quantify any subsequent kidney safety events.
13. Screening supine BP  $\geq 140$  mm Hg (systolic) or  $\geq 90$  mm Hg (diastolic) for participants  $<60$  years; and  $\geq 150/90$  mm Hg for participants  $\geq 60$  years old, following at least 5 minutes of supine rest. If systolic BP is  $\geq 140$  or 150 mm Hg (based on age) or diastolic  $\geq 90$  mm Hg, the BP should be repeated 2 more times and the average of the 3 BP values should be used to determine the participant's eligibility.
14. Screening supine standard 12-lead ECG that demonstrates clinically relevant abnormalities that may affect participant safety or interpretation of study results (eg, QTcF  $>450$  ms or QRS interval  $>120$  ms, complete LBBB, signs of an acute or indeterminate- age myocardial infarction, ST-T interval changes suggestive of myocardial ischemia, second- or third-degree AV block, or serious bradyarrhythmias or tachyarrhythmias). If the uncorrected QT interval is  $>450$  ms, this interval should be rate-corrected using the Fridericia method only and the resulting QTcF should be used for decision making and reporting. If QTcF exceeds 450 ms, or QRS exceeds 120 ms, the ECG should be repeated twice and the average of the 3 QTcF or QRS values used to determine the participant's eligibility. Computer-interpreted ECGs should be overread by a physician experienced in reading ECGs before excluding a participant.

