### Differentiating Acute Kidney Injury from DIKI

A confirmed Screat increase is defined as:

- (i)  $\geq 0.3 \text{ mg/dL} (\geq 26.5 \text{ } \mu\text{mol/L})$  within 48 hours OR
- (ii) confirmed Screat increase  $\geq 1.5$  times baseline (known or suspected to have occurred within the prior 7 days).

Based on the assessments performed, suspected AKI (including DIKI) may be differentiated from DIKI as follows.

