#### Adult participants

	AKI (including DIKI) Any one of the below	DIKI
Scys & Screat	Simultaneous, confirmed serum cystatin C (Scys) increase and confirmed Screat increase	Confirmed Screat increase without confirmed increase in reflex Scys AND Confirmed Screat-based eGFR decrease without confirmed combined Screat-Scys-based eGFR decrease.
eGFR	Decrease in Screat-based eGFR and combined Screat-Scys-based eGFR (when available)	
Albuminuria or proteinuria	Confirmed albuminuria increase (see Appendix 7 for Grades A1 to A3 quantitation)	
Urine volume	Urine volume $<0.5 \text{ mL/kg/h}$ for 6 consecutive hours	

Regardless of the presence or absence of increase in Scrat, DIKI and other causes of AKI may be suspected if either there is (i) new-onset or worsening albuminuria or proteinuria are detected.

All confirmed cases of clinically relevant decrease in kidney function should be considered potential cases of DIKI if no other reason for the kidney function abnormalities has been found.

If appropriate, nephrology consultation may be recommended to facilitate differentiation of renal parenchymal disease, pre-renal azotemia, and post-renal obstruction. All confirmed cases of clinically relevant decrease in kidney function should be considered potential cases of DIKI if no other reason for the kidney function abnormalities has been found.

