**Table 7. Protocol-Required Laboratory Assessments**

Hematology	Chemistry	Urinalysis	Other
Hemoglobin	Urea	Local Dipstick:	COVID-19 testing
Hematocrit	Creatinine	pH	Urine drug screening d
RBC count	Serum cystatin C a	Glucose (qual)	Pregnancy Test e
Platelet count	eGFR, eCrCl b	Protein (qual)	
WBC count	Glucose (fasting)	Blood (qual)	
Total neutrophils (Abs)	Calcium	Ketones	At Screening only:
Eosinophils (Abs)	Sodium	Nitrites	FSH f
Monocytes (Abs)	Potassium	Leukocyte esterase	HBsAg
Basophils (Abs)	Chloride		HBsAb
Lymphocytes (Abs)	Total CO 2 (bicarbonate)	Laboratory:	HCVAb
	AST, ALT	Microscopy and	HIV
MCV	Total bilirubin	Culture c	
MCH	Alkaline phosphatase		
MCHC	Uric acid		
	Albumin		
	Total protein		

- a. Scys: Screening or Baseline Scys is recommended to help differentiate post-baseline DIKI from DICI. Post-baseline, Scys is measured if and only if serum creatinine increase post-baseline is observed (see Section [7.1.1](#)).
- b. Screening and Baseline eGFR or eCrCl is measured with Screat-based formula. Age-specific kidney function calculation (see Section [10.7.2](#)) is recommended to assess presence or absence of post-baseline change in kidney function.
- c. Only if UTI is suspected and urine dipstick is positive for nitrites or leukocyte esterase or both.
- d. The minimum requirement for drug screening includes cocaine, THC, opiates/opioids, benzodiazepines, and amphetamines (others are site- and study- specific).
- e. Local urine testing will be standard for the protocol unless serum testing is required by local regulation or IRB/EC. See [SoA](#) for collection times.
- f. For confirmation of postmenopausal status only in females <60 years old and not using hormonal or HRT only.

The investigator must review the laboratory report, document this review, and record any clinically relevant changes occurring during the study in the AE section of the CRF.

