3.5.2. Laboratory Data

Safety laboratory tests will be performed as described in the protocol. To determine if there are any clinically significant laboratory abnormalities, the haematological, clinical chemistry (serum) and urinalysis safety tests will be assessed against the criteria specified in the sponsor reporting standards. The assessment will not take into account whether each participant's baseline test result is within or outside the laboratory reference range for the particular laboratory parameter.

For both periods, the baseline measurement is the last predose measurement prior to administration of PF-07817883 in each study period. Changes from baseline will be defined as the change between the postdose and baseline measurements.

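### SAP 3.5.2 resets the laboratory baseline before the Period 2 dose, so a creatinine or eGFR shift that began in Period 1 or the itraconazole lead-in drops out of the Period 2 change from baseline

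*Protocol*

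**What the plan says.** SAP 3.5.2 defines the laboratory baseline as follows: "For both periods, the baseline measurement is the last predose measurement prior to administration of PF-07817883 in each study period". It continues: "Changes from baseline will be defined as the change between the postdose and baseline measurements". Abnormalities are handled apart from this; the safety tests "will be assessed against the criteria specified in the sponsor reporting standards", and the SAP does not reproduce those standards.

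SAP 6.5 splits safety data into three intervals: PF-07817883 alone, itraconazole alone (from the first itraconazole dose to just before coadministration on Period 2 Day 4), and the combination from then to the end of the study. It promises summary tables for each. SAP 3.5.4 takes a different line for ECGs: the last value before PF-07817883 in Period 1 is the baseline for both periods.

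The protocol uses the word baseline for kidney function in several places. Exclusion criterion 12 (sections 1.1 and 5.2) has eGFR or eCrCl calculated "to determine eligibility and to provide a baseline to quantify any subsequent kidney safety events". Table 7 footnote b says "Screening and Baseline eGFR or eCrCl is measured with Screat-based formula", and footnote a recommends cystatin C at one or other of those two visits. Section 7.1.1 defines a confirmed creatinine increase as at least 0.3 mg/dL "within 48 hours OR" a rise relative to baseline of at least 1.5-fold. Neither 7.1.1 nor section 10.7.1 names the baseline visit.

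**The concern.** In a fixed-sequence design, everyone reaches the Period 2 dose after the Period 1 dose and three itraconazole doses. A baseline taken at that point answers a narrow question: what changed after PF-07817883 was added. It does not show what changed since the participant was untreated.

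Two things are lost. First, a creatinine or eGFR shift that began in Period 1 or the lead-in and carried on is split at the Period 2 dose, and the Period 2 table shows only the later part. Second, the itraconazole-alone interval has no usable change from baseline. Its values come before the Period 2 baseline, or are that baseline, and the SAP gives no other reference for them.

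This matters most in Period 2, because protocol section 4.2 expects higher PF-07817883 exposure there.

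**Working it through.** The plan states no figure on this point, so there is nothing to reproduce. The check sets the two baselines side by side.

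**Order of events** (protocol section 4.1 and Table 4): PF-07817883 on Study Day 1; itraconazole on Study Days 5, 6 and 7; itraconazole followed by PF-07817883 on Study Day 8 (Period 2 Day 4). A laboratory value just before the second PF-07817883 dose therefore follows one PF-07817883 dose and three itraconazole doses.

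**Formula.** Let F be the creatinine before the first dose, P the value before the Period 2 dose and X the later Period 2 value. The fixed-baseline ratio is X/F. The SAP Period 2 ratio is X/P = (X/F) / (P/F). The reset divides out whatever drift P/F had occurred by then.

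**Illustration** (assumed values): F = 0.80, P = 1.02, X = 1.22 mg/dL on Study Day 12, man aged 40.

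- Fixed: 1.22/0.80 = 1.525, or 1.53-fold.
- Drift: 1.02/0.80 = 1.275.
- SAP Period 2: 1.22/1.02 = 1.196, or 1.20-fold (check: 1.525/1.275 = 1.196).

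eGFR uses the male creatinine-only equations in section 10.7.2.1, 142 × (Screat/0.9)^a × 0.9938^40, with a = −0.302 up to 0.9 mg/dL and a = −1.200 above it:

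| Creatinine (mg/dL) | eGFR (mL/min/1.73 m²) |
|---|---|
| 0.80 | 114.7 |
| 1.02 | 95.3 |
| 1.22 | 76.9 |

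From the fixed baseline, eGFR falls from 114.7 to 76.9, a change of −33%. From the SAP Period 2 baseline it falls from 95.3 to 76.9, a change of −19%.

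**Range.** The gap depends entirely on the assumed drift. For a 1.5-fold rise from the fixed baseline, the SAP Period 2 table shows:

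| Drift P/F | Change shown |
|---|---|
| 1.00 | +50.0% |
| 1.10 | +36.4% |
| 1.20 | +25.0% |
| 1.25 | +20.0% |
| 1.30 | +15.4% |

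With no drift the two baselines agree. The reset can also exaggerate: for values of 1.00, then 0.80, then 1.20, the fixed ratio is 1.20 and the SAP Period 2 ratio is 1.50.

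**Limit.** The safety-laboratory columns in protocol Tables 1 and 3 are damaged in the text available here, so the sampling days used above are assumptions. If no laboratory sample precedes the dose on Period 2 Day 4, the last earlier value would serve as the Period 2 baseline and would capture less of the lead-in.

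**The case against.** The best defence is that per-period baselines are an ordinary choice in multi-period studies and isolate the effect of the dose just given. Nothing is deleted. Laboratory values are listed and summarized by treatment (SAP 6.5.2), so a lead-in rise is visible as absolute values, and a rise within Period 1 appears as a change in the Period 1 table. This stands, and it is why the per-period change should be kept. It does not supply a change from the untreated state for either Period 2 interval, and the SAP's own ECG rule shows that a fixed baseline fits this design.

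Three stronger readings are tempting, and the documents do not support them.

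- A reader might infer that a 1.5-fold creatinine rise is a kidney event that the SAP table downgrades. Section 7.1.1 makes it a confirmed creatinine increase that needs evaluation. The acute kidney injury column asks for more, such as "Simultaneous, confirmed serum cystatin C (Scys) increase and confirmed Screat increase", or offers alternatives based on eGFR, albuminuria or urine volume. SAP 3.5.2 defines no kidney event and reclassifies no site finding. A 1.5-fold rise noted at the site and a 20% change in a table can both be correct.
- A reader might infer that a screening value is too old to serve as baseline because 7.1.1 speaks of 1.5 "times baseline (known or suspected to have occurred within the prior 7 days". That phrase dates the rise, not the baseline sample. Read the other way, it would also rule out Day -1, which is 12 days before Study Day 12.
- A reader might infer that criterion 12 firmly fixes the screening value as the kidney baseline. Its reference to screening is attached to the participant's age, so the visit is unclear rather than settled.

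**Conclusion.** The point holds as a minor one about the safety tables. SAP 3.5.2 takes its Period 2 laboratory baseline after earlier exposure to both drugs, and it leaves the itraconazole-alone interval without a change from baseline. In the illustration, a 1.53-fold rise is shown as 1.20-fold. That size rests on invented values with a 27.5% rise before the Period 2 dose; the documents give no basis for expecting such a drift, and without drift the difference is zero.

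The consequence is limited. Kidney AE grading in section 10.7.3 uses absolute eGFR bands and does not depend on the baseline. The 0.3 mg/dL criterion looks at a 48-hour window and needs no fixed visit. The primary PK analysis and the sample size are untouched.

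The unnamed baseline visit in the protocol is a separate matter of wording. It should be reconciled, but this review takes no view on which visit governs clinical evaluation.

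**What to change.** In SAP 3.5.2, keep the per-period change and add that creatinine and creatinine-based eGFR change will also be presented, for the itraconazole-alone and coadministration intervals of SAP 6.5, from the last value before the first PF-07817883 dose in Period 1. That value is already the SAP's Period 1 laboratory baseline, so the cost is one sentence and one extra summary column, with no new creatinine samples. The addition should stay with creatinine-based eGFR: Table 7 footnote a allows cystatin C at either screening or baseline, so a combined estimate may not exist at that visit.

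Separately, the sponsor should reconcile the use of baseline in criterion 12 (sections 1.1 and 5.2), sections 7.1.1 and 10.7.1, Table 7 footnotes a and b, and SAP 3.5.2. This costs wording only.
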